## *2.2. Study visits pregnancy*

A broad risk evaluation will be performed in participating females at the initial contact (V1) including: evaluation of maternal age, parity, history of GDM in previous pregnancies, detailed family history, ethnicity, preconceptional diseases, obstetric history. Height (stadiometer measured to the nearest centimeter) and actual weight (calibrated scales, no clothes) will be additionally assessed. Moreover, an evaluation of preconceptional weight (self-reported) and BMI as well as measurement of blood pressure will be performed. All patients receive medical nutrition therapy (isocaloric diet containing 40-50% carbohydrates, 20% proteins and 30-35% fat, divided into three meals and three snacks) and lifestyle advice for 30 minutes following international recommendations and are advised on capillary blood glucose measurement (fasting as well as 1h after starting each meal) at the initial visit (V1). Randomisation will be done after a run-in period of 6 to 8 days (V2). The run-in period is omitted for patients who had a diagnosis of GDM before 24+0 according to the local guidelines and already received medical nutrition therapy, lifestyle intervention and advices on capillary blood glucose measurements. The third visit (V3) will be scheduled 8 to 10 days after V2 and further follow-up visits every two weeks (i.e. 12 to 16 days after each visit). HbA1c and glycosylated fibronectin, hsCRP, proBNP, Troponin T, will be assessed at V2 as well as at the first visit between 36+0 and 38+6 weeks of gestation (12 ml, non-fasting state) (V4). Detailed fetal ultrasound examinations, a detailed examination of dietary intake as well as a blinded CGM (control group only) will be performed at V2 and V4. Body weight change and use of glucose lowering medications (amount of insulin units) will be examined at every visit. At every follow-up visit glucose measurements (SMBG or rt-CGM) and routine ultrasound examinations (fetal biometry and umbilical artery doppler) will be evaluated by the medical staff and all patients will be treated according to the standard of care for patients with GDM. This includes lifestyle modification and insulin therapy if recommended thresholds are exceeded. Both groups will be treated to be in the target range between 65 to 140 mg/dl [3.6 to 7.8 mmol/l] with at least 8h fasting glucose levels equal or below 95 mg/dl [5.3 mmol/l] and 1h postprandial glucose

measurements equal or below 140 mg/dl [7.8 mmol/l] in accordance with the CONCEPTT study and the ADA recommendations, respectively. Intermediate acting neutral protamine Hagedorn (NPH) insulin is started in the evening if  $\geq 2$  measurements of fasting glucose are equal or above 95 mg/dl [5.3 mmol/l] in a period of one week and rapid acting insulin analogues (Aspart or Lispro) if  $\geq 2$  measurements of 1h postprandial glucose (either after breakfast, lunch or dinner) are equal or above 140 mg/dl [7.8 mmol/l] in a period of one week. NPH is started with 6 to 10 IU and increased by 4 IU (or in case of higher doses i.e.  $> 25$  IU by 20%) and rapid acting insulin is started with 2 to 4 IU and increased by 2 to 4 IU if thresholds are not achieved within three days. Long acting insulin analogues such as glargine (U100/U300) or detemir can be used as an alternative to NPH if necessary. Patients are trained on insulin management and titration according to their glucose levels. Metformin can be used according to local practice guidelines (recommended in Sweden but not in Austria, Germany or Switzerland as first-line pharmacological intervention).

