### *2.5. Control group*

The control group participants will perform self-monitored blood glucose testing with a study-provided blood glucose meter, including testing supplies. They will perform capillary blood glucose monitoring as routinely used for patients with GDM, i.e., at least four capillary blood glucose values daily including measurements at fasting as well as 1h after starting each meal by using a routinely available blood glucose measurement device. The study participants will keep a log book of their glucose values, which will be reviewed by clinicians from the study team at each visit and used for lifestyle and dietary recommendations as is routinely done in clinical practice. From V2 to V3 as well as once for ten days between 36+0 and 38+6 the control group receive blinded CGM; neither patients nor the treating medical staff will have access to the data recorded by the CGM sensor at this point in time. Instead, patients will control blood glucose levels based on SMBG, as is the routine procedure in current GDM treatment. Otherwise, the control group will receive the same study assessments as the intervention group. The blinded CGM will be removed and returned to Dexcom after the 10 day wear period after CGM data is uploaded to CLARITY® by an unblinded investigator who must not communicate about the results with patients or medical staff.

Each participant in the control group will be assigned a study blood glucose meter to measure and store their blood glucose values during the study. Therefore, the Contour® Next One system will be used. The meter has CE Mark clearance and is commercially available in Europe. Participants will receive an ample supply of meter test materials based on quantities routinely used. A commercially available desk-top software (Diabass® Pro), used in conjunction with Contour® Next One system glucose meter for blood glucose monitoring, will be utilized for downloading the meter data by the sites at V3 and V4 after checking that dates and times are correct.

Blood glucose meters used by the control group will be assessed to establish frequency of testing (overall and per week) as well as percentage of days with lower than four measurements per day.

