### 3. Sample Size and Statistical Analysis

#### 3.1. Sample size

With a sample size of n=338 (169 women per group) we will be able to detect a difference between two independent proportions of LGA of 13.7% vs 25.8% (according to the results of a previous study) with a power of 80% and a two-sided type 1 error of  $\alpha=0.05$  (calculated for Pearson's chi-square test). Considering a drop-out rate of 10% a total sample size of n=372 (186 women per group) is necessary for this study. This is in line with the sample size suggested by Kestilä et al.. A blinded sample size review (the proportion of LGA cases in the sample is reviewed) and adaptation is planned after 50% of the patients have been investigated. The sample-size calculation was performed by using the software G\*Power (V3.1.9.2).

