#### 3.2. Analysis plan

Analyses should be conducted on the intention-to-treat principle. Categorical variables will be summarized by counts and proportions; continuous variables data will be summarized by means and standard deviations (SD) or by median and interquartile range in the case of strong deviations from the normal distribution. Pearson's chi-square test will be used to compare differences in the primary outcome (difference in proportion of LGA newborns) and for binary secondary outcomes (such as caesarean section rate, shoulder dystocia and neonatal hypoglycaemia). Bernard's test will be used as an alternative if an expected frequency in contingency tables is equal or less than 5 and the Cochran-Mantel-Haenszel method will be used as sensitivity analysis to adjust for possible center specific effects. Continuous secondary outcome parameters (such as mean glucose, duration and amount of hyperglycaemia, glycaemic variability and other CGM measures, postpartum OGTT data, HbA1c, glycosylated fibronectin, hsCRP, proBNP, Troponin T, or anthropometric data of the newborn) will be compared by student's t-test. Rank based inference (such as the Brunner-Munzel test) will be used as an alternative in case of skewed distributed parameters. The association between HbA1c, CGM measures and delivery and risk of LGA offspring will be assessed by binary logistic regression. There are many possible objectives for which analysis could be performed in this study (e.g. functional principal components analysis for CGM data). Hence, the present analysis plan represents only a selection of methods, which will be used for analysing the main objectives. Risk and time preferences will be analysed by non-parametric and parametric methods. In particular, we plan to fit the choice data to a CRRA (constant relative risk aversion) utility function. Associations between risk and time preferences and behaviour (dietary patterns and physical activity) will be investigated. For the health economic evaluation, incremental cost-effectiveness and cost-utility ratios (ICER/IUCR: additional cost per additional LGA

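### CGM outcomes are compared by tests that use no pre-randomisation glucose value, which gives up precision on secondary outcomes

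*Combined protocol and SAP*

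**What the plan says.** **Before allocation.** Under section 2.2 all women "are advised on capillary blood glucose measurement (fasting as well as 1h after starting each meal) at the initial visit (V1", and then "Randomisation will be done after a run-in period of 6 to 8 days (V2". The run-in is dropped for women diagnosed before 24+0 who have already had diet, lifestyle and self-measurement advice. HbA1c is measured at V2. The diagnosis itself rests on an OGTT (section 2.1).

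**Sensors.** The rt-CGM arm receives its sensor at V2 (section 2.5, Intervention). Controls wear a blinded sensor from V2 to V3 and once more between 36+0 and 38+6 (section 2.5, Control group). There is therefore no CGM baseline in either arm.

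**Capillary data kept for the study.** The Control group section says "Each participant in the control group will be assigned a study blood glucose meter", and the software "will be utilized for downloading the meter data by the sites at V3 and V4". Both visits fall after randomisation. No section mentions storing the run-in readings of either arm as trial data. The synopsis does have staff evaluate glucose measurements at every visit.

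**Analysis.** Section 3.2 takes "Continuous secondary outcome parameters (such as mean glucose, duration and amount of hyperglycaemia, glycaemic variability and other CGM measures", among others, and assigns them Student's t-test, with a rank method such as Brunner-Munzel for skewed variables. No covariate is named. Section 2.4 minimises on gestational week, previous GDM and BMI class, none of which is a glucose value.

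**The concern.** Section 1.2 names better maternal glycaemic control as a hypothesis, and the CGM measures listed in section 1.3 are its most direct test. Women differ in glucose level before they are allocated. If that difference carries over into the CGM periods, an unadjusted comparison leaves it in the error term, and a model with a pre-randomisation glucose value removes part of it.

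The sample size was set for LGA alone, and no power, SD or target difference is stated for any CGM outcome. How precisely these outcomes are estimated therefore depends on the method chosen in section 3.2. At stake are wider confidence intervals, and a greater chance of missing a true glycaemic difference, than the collected data require.

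**Working it through.** **1. The plan's own figure.** Section 3.1 sizes the trial to "detect a difference between two independent proportions of LGA of 13.7% vs 25.8"%, "with a power of 80% and a two-sided type 1 error of" 0.05. With the pooled-variance formula, n per arm = [1.960 × √(2 × 0.1975 × 0.8025) + 0.842 × √(0.137 × 0.863 + 0.258 × 0.742)]² / (0.258 − 0.137)², which gives 169 per arm, 338 in total, with power 80.1%. The stated figure reproduces. It concerns LGA and does not enter this point except as the number of evaluable women.

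**2. Inputs for the CGM outcomes.** n = 169 per arm, two-sided 0.05 and 80% power are from section 3.1. The correlation r between a baseline glucose value and a later CGM measure is not in the documents; I assume 0.2 to 0.7. No SD is given, so results are in SD units.

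**3. Formulas.** ANCOVA multiplies the variance of the arm difference by 1 − r².
- Fall in standard error: 1 − √(1 − r²).
- Detectable difference: (1.960 + 0.842) × √(2/169) × √(1 − r²). Unadjusted: 2.802 × 0.1088 = 0.305 SD.
- Equivalent women per arm without adjustment: 169 / (1 − r²).
- Power for an illustrative 0.25 SD difference (normal approximation): Φ(0.25 / √(2(1 − r²)/169) − 1.960).

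| r | 1 − r² | Fall in SE | Detectable difference (SD) | Equivalent n per arm | Power at 0.25 SD |
|---|---|---|---|---|---|
| none | 1.00 | – | 0.305 | 169 | 63% |
| 0.2 | 0.96 | 2.0% | 0.299 | 176 | 65% |
| 0.3 | 0.91 | 4.6% | 0.291 | 186 | 67% |
| 0.4 | 0.84 | 8.3% | 0.279 | 201 | 71% |
| 0.5 | 0.75 | 13.4% | 0.264 | 225 | 76% |
| 0.6 | 0.64 | 20.0% | 0.244 | 264 | 82% |
| 0.7 | 0.51 | 28.6% | 0.218 | 331 | 90% |

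**4. Incomplete baseline.** If a share q of women have the baseline value, the variance factor is roughly 1 − q r². At r = 0.5 the fall in SE is 13.4% with q = 1, 10.6% with q = 0.8 (√0.80 = 0.894) and 7.8% with q = 0.6 (√0.85 = 0.922). This matters for run-in readings, which some women will not have.

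**5. How much comes from which source.** For two covariates, R² = (a² + b² − 2abc)/(1 − c²). Here a is the correlation of HbA1c with the outcome, b that of the run-in readings, and c the correlation between the two covariates. All three are assumed.
- a = 0.4, b = 0.5, c = 0.5: R² = 0.21/0.75 = 0.28. The SE falls by 8.3% with HbA1c alone and by 15.1% with both.
- a = 0.4, b = 0.6, c = 0.4: R² = 0.328/0.84 = 0.39. The SE falls by 8.3% with HbA1c alone and by 21.9% with both.

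On these assumptions, part of the gain is available from HbA1c, which is already collected. Run-in readings add to it but are not its only source.

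**The case against.** **The correlation may be low.** Sections 2.2 and 2.2's continuation on insulin describe treatment of both arms to the same glucose range, with insulin started after repeated readings above threshold. High run-in values thus lead to treatment that lowers later glucose, most of all by V4. A few fasting and post-meal readings also say little about night-time hypoglycaemia or variability. This stands. It is why the range starts at 0.2, where the gain is slight, and why a single r should not be read as applying to every CGM measure. If r were zero, nothing would be gained.

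**Run-in data will be incomplete.** Some women have no run-in, and section 1.1 itself describes poor adherence to self-measurement as a real problem in GDM. This also stands, and it favours HbA1c as the main covariate.

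**Section 3.2 says that it lists only some of the methods.** It does, but it presents them as the ones meant for the main objectives. In an open-label trial, an adjusted model chosen after data have been seen is open to challenge; one written down beforehand is not.

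**Stronger readings that the documents do not support.** A reader might infer that the run-in readings are thrown away. The documents are only silent: staff review glucose at every visit, and the eCRF content is not shown. A reader might also infer that chance imbalance in baseline glucose biases the comparison. Under randomisation it does not; the standard error of the t-test already allows for it, and the type I error is not inflated.

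**Conclusion.** The point holds as one of efficiency. The stated tests for CGM outcomes, parametric or rank-based, use no pre-randomisation glucose value, although V2 HbA1c is collected in all women and most also take capillary readings before allocation. The loss falls on secondary outcomes that carry a named hypothesis.

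Its size depends on an assumed correlation and on complete baseline data. It runs from negligible at r = 0.2 to substantial at r = 0.7, and shrinks if baseline values are missing. The direction is secure for any non-zero correlation; the magnitude is not. Neither the validity of the comparisons nor the primary LGA analysis is in question, and the loss should not be ascribed to the run-in readings alone.

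**What to change.** In section 3.2, pre-specify linear regression (ANCOVA) of the continuous CGM outcomes on arm, with V2 HbA1c and the minimisation factors (gestational week, previous GDM, BMI class) as covariates. Keep the t-test or rank test as a sensitivity analysis. That also covers measures with many zeros, such as time in hypoglycaemia, where a log transform may fail. This part needs no new data and costs a sentence or two in the plan.

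As a cheap addition, enter each woman's mean fasting and mean 1-h postprandial capillary glucose over the run-in in the eCRF at V2. Take the values from her own records, before allocation and in both arms, and add the two means as covariates. State in advance a missing-indicator or mean-imputation rule for women without a run-in or with incomplete readings. Extra study meters are not needed. The cost is one eCRF entry per woman and some missing baseline values to handle.

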## 2. Research Design and Methods

### 2.1. Participants and recruitment; Exclusion criteria

This study is designed as an open-label multicentre randomized controlled trial with two parallel groups including a total of 372 female patients (n=186 with rt-CGM, n=186 with SMBG) with recent diagnosis of GDM. Diagnosis of GDM (i.e. diabetes first diagnosed in second and third trimester and not clearly type 1 or type 2 diabetes) is made in accordance with the IADPSG criteria after 24+0 weeks of gestation by a 2h 75g OGTT. If the GDM diagnosis is made before 24+0 weeks of gestation in accordance with the local guideline (i.e. when IADPSG cut-offs for fasting and post-load glucose are exceeded) patients can be included if no insulin treatment was started until 24+0^21. The study will be conducted at four tertiary referral centres in Austria, Switzerland, Sweden and Germany. All pregnant females (aged between 18 and 55 years) will be consecutively recruited after diagnosis of GDM until 31+6 weeks of gestation among women visiting the pregnancy outpatient departments (Division of Obstetrics and feto-maternal Medicine, Medical University of Vienna; Division of Obstetrics, University Hospital Basel, Clinic of Obstetrics, Charité Berlin, Clinic of Obstetrics, University Hospital Jena) or the diabetes outpatient departments (Division of Endocrinology and Metabolic Diseases at the Heinrich Heine University, Düsseldorf; Department of Medicine, University Hospital, Örebro).

Exclusion criteria are:

Overt diabetes (i.e. pregestationally known type 1 or type 2 diabetes or fasting plasma glucose during the OGTT  $\geq 126$  mg/dl [7.0 mmol/l] or HbA1c  $\geq 6.5\%$  [44 mmol/l] or 2h post-load OGTT levels  $\geq 200$  mg/dl [11.1 mmol/l] assessed before 24+0 weeks of gestation, whereby results need to be confirmed by repeated testing in case of unequivocal hyperglycemia according to the ADA standards); History of bariatric surgery or other surgeries that induce malabsorption; Long-term use (>2 weeks) of systemic steroids prior to enrolment; Multiple pregnancy; Patients already using glucose lowering medications (metformin or insulin) before study entry; fetal growth restriction due to placental dysfunction at study entry; Inpatient psychiatric treatment up to 1 year before enrolment; Participation in this study in previous pregnancy;

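### Record before allocation at V2 whether the insulin rule is already met, and use it when analysing start and amount of therapy: a cheap gain in precision for one secondary outcome

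*Combined protocol and SAP*

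**What the plan says.** **Timing.** Section 2.2 says that women "are advised on capillary blood glucose measurement (fasting as well as 1h after starting each meal) at the initial visit (V1"). Randomisation follows at V2: "Randomisation will be done after a run-in period of 6 to 8 days (V2"). One group skips this interval: "The run-in period is omitted for patients who had a diagnosis of GDM before 24+0 according to the local guidelines", provided they have already had nutrition therapy, lifestyle intervention and advice on self-monitoring.

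**Eligibility.** Section 2.1 excludes "Patients already using glucose lowering medications (metformin or insulin) before study entry", and section 2.4 equates study entry with V1. For a diagnosis before 24+0, "patients can be included if no insulin treatment was started until 24+0".

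**Treatment rule.** Section 2.2 starts evening insulin if at least two "measurements of fasting glucose are equal or above 95 mg/dl [5.3 mmol/l] in a period of one week". It has a matching rule for 1h values at or above 140 mg/dl. For metformin it gives no threshold: "Metformin can be used according to local practice guidelines".

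**What is captured.** The Synopsis has staff evaluate glucose measurements at every visit. Section 2.2 adds that "use of glucose lowering medications (amount of insulin units) will be examined at every visit".

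**Outcome and analysis.** Section 1.3 lists initiation and dose of glucose-lowering treatment among the secondary outcomes. Section 1.4 asks whether CGM data changes how many women need drug treatment. Section 3.2 names chi-square, t-test and rank-based comparisons for secondary outcomes, with Cochran-Mantel-Haenszel (CMH) by centre as a sensitivity analysis. It describes itself as a partial list.

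**The concern.** The run-in of 6 to 8 days is about as long as the one-week window of the insulin rule. Some women may therefore have a treatment indication by V2 that owes nothing to the device. Most of them should be treated in either arm, so they add variance to the comparison of therapy starts and little information about rt-CGM.

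This status is a natural stratification variable, but only if it is a true baseline variable. In an open-label trial that means fixing it before the arm is known. The protocol does not set that order, and status is not among the minimisation factors in 2.4 (gestational week, previous GDM, BMI class). At stake is the width of the interval for one secondary outcome, which bears on the section 1.4 question.

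**Working it through.** **1. The plan's own figure.** Section 3.1 gives 25.8% vs 13.7% LGA, 80% power and two-sided 0.05. The mean proportion is 0.1975.

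n = [1.960 × √(2 × 0.1975 × 0.8025) + 0.842 × √(0.258 × 0.742 + 0.137 × 0.863)]² / 0.121² = 168.8, so 169 per group, as stated. The point below does not change this. I use 169 per arm throughout.

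**2. Can the rule be met before allocation?** Yes. Self-monitoring begins at V1, the rule needs two raised values of one type in one week, and V2 comes 6 to 8 days later. The drug exclusion stops at V1, so meeting the rule in the run-in excludes no one. Where the run-in is omitted, women already on a drug are excluded, but an untreated woman may have met the rule on earlier readings.

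**3. Inputs for the size (all assumed).** No document gives:
- q, the share meeting the rule by V2;
- s, the share of those women who start treatment;
- p1 and p0, the later start rates in the other women (rt-CGM and SMBG).

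**4. Formulas.** Overall start rates are P1 = qs + (1 − q)p1 and P0 = qs + (1 − q)p0. Approximately:
- unstratified SE = √{[P1(1 − P1) + P0(1 − P0)] / n}
- stratified SE = √{[2q·s(1 − s) + (1 − q)(p1(1 − p1) + p0(1 − p0))] / n}

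Example: q = 0.10, s = 1, p1 = 0.20, p0 = 0.10. Then P1 = 0.28 and P0 = 0.19.
- Unstratified: √[(0.2016 + 0.1539)/169] = 4.59 points.
- Stratified: √[0.9 × (0.16 + 0.09)/169] = 3.65 points.
- Reduction: 1 − 3.65/4.59 = 20%.

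**5. Results by simulation.** The closed form agrees to within about one percentage point for the four rows with error-free status. SE reductions are for q = 10/20/30%; power is at q = 20%.

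| Later starts, rt-CGM vs SMBG | Share of indicated women who start | SE reduction | Power, unstratified to CMH by status |
|---|---|---|---|
| 20% vs 10% | 100% | 20/32/39% | 35% to 64% |
| 35% vs 20% | 100% | 11/19/25% | 61% to 79% |
| 35% vs 20% | 80% | 6/10/12% | 63% to 72% |
| 50% vs 35% | 80% | 2/5/6% | 59% to 64% |
| 20% vs 10%, status recorded with 75% sensitivity and 95% specificity | 100% | 8/15/18% | 35% to 46% |

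**6. Same quantity estimated.** In the first row the mean all-women difference is 9.0/8.0/7.0 points, and the mean Mantel-Haenszel risk difference is the same. With equal later start rates of 15% in both arms, the type I error of the CMH test is 0.049 to 0.050.

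**7. Insulin amount.** Adjustment multiplies the SE by √(1 − R²). If status explains 5/10/20% of the variance (assumed), the factor is 0.975/0.949/0.894, a reduction of 2.5/5/11%.

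**The case against.** The strongest reply is that no error has been shown. An unadjusted test of a secondary outcome is legitimate, and the same precision argument could be made for HbA1c with its V2 value or for the minimisation factors. That stands, and it is why this is an improvement and not a defect. Therapy start differs in one respect: the treatment rule itself ties V2 status to the outcome.

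Much of the V2 review is already in the protocol, since glucose values are evaluated and drug use is examined at every visit. That also stands. What remains is the order relative to allocation, rule status as distinct from drug use, and a named analysis. The eCRF, which section 4.2 only mentions, may already settle the first two.

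The size is uncertain. Low later start rates favour stratification, and the gain shrinks as those rates rise or as fewer indicated women start. Status will also be imperfect. Section 1.1 acknowledges poor reliability and adherence in self-monitoring, and the study meter and its download are described only for the control group after randomisation. The table covers these cases. If 'start' is analysed as time to therapy, the CMH figures do not apply.

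A reader might infer that women treated or indicated before V2 bias the trial or should be excluded. The documents do not support this. Status arises before randomisation and is balanced in expectation, so the all-women comparison is unbiased. A reader might also infer that V2 decisions are made with the arm known. The protocol leaves the order open, so this cannot be asserted.

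**Conclusion.** The point holds as a minor, precision-only improvement for one secondary outcome. The facts about timing, eligibility and the insulin rule follow directly from sections 2.1, 2.2 and 2.4. That nothing requires recording before allocation, and that no named analysis uses the status, holds for the documents available; 3.2 does not claim to be complete.

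Over the assumed scenarios with error-free status and q between 10 and 30%, the SE for therapy starts falls by between 2 and 39%. The upper end needs low later start rates and treatment of every indicated woman. With the assumed recording error, that same scenario gives 8 to 18%. If q is near zero there is practically no gain. The LGA primary outcome, the sample size and the validity of the intention-to-treat comparison are not affected.

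**What to change.** Leave eligibility and the treatment rule as they are.

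**Section 2.4.** Require that, before the MUW Randomizer is opened at V2, the eCRF records:
1. whether the section 2.2 insulin rule is met on the available self-monitoring values (yes/no; too few readings to judge is coded 'no');
2. whether any glucose-lowering drug has been started or decided (yes/no, and which drug). This covers metformin, which has no stated threshold.

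Status is 'yes' if either item is 'yes'.

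**Section 3.2.** Keep all randomised women. Compare therapy starts with the CMH test stratified by this status and report the Mantel-Haenszel risk difference. Adjust insulin amount for status. Keep CMH by centre as the separate sensitivity analysis.

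**Cost.** Two short eCRF entries, a fixed order of steps at V2 and a few lines in 3.2. No extra visit, test or change of care is needed. If the eCRF already holds these items, the sponsor need only state the order and name the analysis. The order of entry cannot be restored for women already randomised.
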